8.2.5. Multiplicity issues

The overall type-I error rate will be controlled at the two-sided 0.05 level using a hierarchical testing procedure. The primary endpoints will be tested sequentially in the order described in [Section 8](#). The secondary endpoints will be tested following the hierarchical testing procedure with a pre-specified order, that is, inferential conclusions about successive secondary endpoints require statistical significance at 0.05 significance level of the previous one.

The following secondary endpoints will be included in the multiplicity adjustment scheme and tested in the following order:

- Change from baseline to Week 24 in global lung UCSF Mucus Scoring
- Percent change from baseline to week 24 in trimmed distal [s]iRaw at TLC

Each endpoint will be tested at 0.05 (two-sided) level of significance. If at any step the null statistical hypothesis of no study intervention difference is not rejected, the endpoints listed after that step will be reported at nominal level, otherwise will be technically eligible for being declared significant.

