The main reason for amended protocol 03 is evolving interest to evaluate FeNO as an airway inflammatory biomarker related to structural lung changes. Therefore, the primary endpoint FEV_1 is proposed to be replaced with the secondary endpoint of FeNO, leading to an overall reduction in sample size.

Protocol amendment summary of changes table

Section # and Name	Description of Change	Brief Rationale
Section 1.1 Synopsis	Information from various literature sources for FeNO assessment added.	To support the rationale for promoting FeNO to a primary endpoint.
Section 2 Introduction	The following text is deleted "and effect on lung function, airway inflammation and the relationship between imaging dynamics and FeNO, and the link with asthma control as perceived by the patient"	The text has been deleted as it is a redundant information.
Section 1.1 Synopsis Section 3 Objectives and Endpoints	The primary endpoint pre-BD FEV_1 has been replaced by FeNO.	To update primary objective to assess the role of dupilumab on airway inflammation related to structural changes in the lung in addition to imaging.
Section 1.1 Synopsis Section 3 Objectives and Endpoints	Minor clarifications on the terminology of the primary and secondary functional respiratory imaging (FRI) endpoints.	To more accurately describe the FRI endpoints.

Section # and Name	Description of Change	Brief Rationale
Section 1.1 Synopsis Section 3 Objectives and Endpoints	Following endpoint has been moved from primary to secondary 
Change from baseline to Week 24 in pre-bronchodilator FEV₁	To reflect the shift of this endpoint from primary to secondary.
Section 1.1 Synopsis Section 3 Objectives and Endpoints	Following endpoint has been moved from tertiary/exploratory to secondary and updated as follows: 
Change from baseline to Week 24 in global lung mucus scoring (UCSF mucus scoring)	This change is proposed due to the increased interest in the assessment of presence of mucus plugs in the airways.
Section 1.1 Synopsis Section 9.2 Sample Size Determination and Preservation of Type I Error For The Primary Endpoints	The text is updated for sample size calculation. New text added for power calculation and hypotheses for the new primary endpoint.	Updates to the sample size calculation and hypotheses reflecting the change to the primary endpoint.

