1 PROTOCOL SUMMARY

1.1 SYNOPSIS

Protocol title:

Randomized, double blind, placebo controlled study to evaluate the effect of dupilumab on airway inflammation through assessments of lung function, mucus plugging and other lung imaging parameters in patients with asthma

Short title:

VESTIGE

Rationale:

Chronic airway inflammation is a characteristic feature of asthma (1). Chronic inflammation is associated with mucus production, airway smooth muscle contraction and hypertrophy, airway hyperresponsiveness, and structural airway remodeling (2).

Although the pathophysiology of airway remodeling in asthma remains to be fully elucidated, key type 2 cytokines are believed to be involved in this process: IL-13 upregulate levels of fractional exhaled nitric oxide (FeNO) (3), which also affects airway smooth muscle function and mucus production, and may influence subepithelial fibrosis by secretion of periostin and other pro-fibrotic mediators. These effects may contribute to airway remodeling and obstruction (4).

IL-13 is implicated in tissue effects on goblet cells and airways smooth muscle cells, which impact on mucus secretion, smooth muscle contractility, and basement membrane thickening (5).

Airway remodeling in established asthma is poorly responsive to current therapies, such as inhalation of corticosteroids and administration of β 2-agonists, anti-leukotrienes, theophylline, and biologics (6, 7). It is plausible that some potentially meaningful airway responses/changes involved in airway remodeling could fail to be detected or demonstrated due to the poor sensitivity of the conventional parameters utilized in these previous clinical studies.

Patients with normal forced expiratory volume in 1 second (FEV₁) can have regional airway structure changes. Functional imaging (FI) is a useful tool for sensitive assessment of structural and functional changes in the lungs after asthma treatment (8). According to previous studies (8, 9, 10, 11) functional respiratory imaging (FRI) technology has demonstrated a higher sensitivity to detect the effect of treatment on lung function than conventional assessments like FEV₁.

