non-invasive biomarker that identifies IL-4/13 mediated airway inflammation at the level of the respiratory epithelium, leading to increased production of NO, which can be measured as FeNO, and is associated with pro-inflammatory effects, including excess mucus production, airway remodeling, and increased bronchoconstriction (12, 13, 14). This inflammatory cascade could be identified via imaging including reduced airflow and increased airway wall thickness, as well as IL-13-mediated goblet cell production. Therefore, airway structural changes and FeNO levels could represent different biomarker components of IL-4 and IL-13 driven inflammation. FeNO has been shown to be a possible predictor of exacerbation risk and accelerated lung function decline and may indicate ongoing damage, although further investigations into this process are warranted (15, 16, 17, 18, 19, 20).

It is hypothesized that the changes in FEV₁ observed with dupilumab treatment are potentially related to reduction in airway inflammation and changes in airway volumes detectable by functional respiratory imaging.

The goal of this study is to gain further insight into the effect of dupilumab on lung inflammation, and also explore the effect on airway changes, biomarkers, and gain preliminary understanding of the potential interrelationships between these parameters.

A combination of classical lung function, patient-reported outcome parameters, and FI methods has the potential to enhance the description of the mode of action of new compounds (8). In addition, results from the recently published ATLANTIS study suggest that a combination of biomarkers (FeNO), physiological testing (FEV₁), and imaging approaches provides a comprehensive assessment of small airway dysfunction (SAD) in asthma (21).

The QUEST study (22) has shown significant and clinically meaningful effect of dupilumab on FEV₁ improvement, particularly in the high blood eosinophil count (≥ 300 cells/mm³) population at baseline, as early as Week 2 and was sustained throughout 52 weeks.

Dupilumab also has the potential to exert an unplugging effect on the airways by reducing mucus production, due to the anti-inflammatory effect via direct inhibition of IL-4 and IL-13 signaling (3, 4, 5).

Therefore by utilizing imaging results, coupled with clinical outcomes (FEV₁), biomarkers (FeNO), and patient-reported outcomes [ACQ, and AQLQ(S)], the study is expected to further characterize dupilumab's unique mechanism of action (MoA).

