4. GENERAL STATISTICAL CONSIDERATIONS

4.1. Sample size

In order to preserve the type I error at 0.05 level for the two primary endpoints, a hierarchical testing procedure will be applied at a 2-sided 5% significance level. The hierarchy of the tests for primary endpoints will be:

1. Proportion of participants achieving response of FeNO <25 ppb at Week 24
2. Percentage change from baseline to Week 24 in untrimmed distal [s]iVaw at TLC

After the significance has been achieved for 2 primary endpoints, the other selected secondary endpoints will be tested following a hierarchical testing procedure at a 2-sided 5% significance level. The whole list of secondary endpoints to be tested in the hierarchical order will be specified in [Section 8.2.5](#).

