8. EFFICACY ANALYSIS

Efficacy analyses will be performed on the ITT analysis set.

Participants will be analyzed for efficacy according to the study intervention group to which they are allocated by the IRT according to the randomization schedule at the randomization visit (as randomized), irrespective of the study intervention actually received.

For all efficacy analyses, time window will be used to assign the visit (see [Section 15.5](#)).

For the analysis of primary objective in the study intervention period,

- The null statistical hypothesis tested is that 1) the proportion of participants achieving response of FeNO <25 ppb at Week 24 is the same between dupilumab and placebo group; 2) the percentage change from baseline in untrimmed distal [s]iVaw is the same between dupilumab and placebo group.
- The alternative statistical hypothesis tested is that 1) the proportion of participants achieving response of FeNO <25 ppb at Week 24 is different between dupilumab and placebo group; 2) the percentage change from baseline in untrimmed distal [s]iVaw is different between dupilumab and placebo group.

In order to preserve the type I error at 0.05 level for the two primary endpoints, a hierarchical testing procedure will be adopted. The tests will be performed in this order:

1. Proportion of participants achieving response of FeNO <25 ppb at Week 24
2. Percentage change from baseline to Week 24 in untrimmed distal [s]iVaw at TLC

All efficacy measurements collected during the study will be considered for analyses, including those obtained after IMP discontinuation, except if study intervention discontinuation was due to the COVID-19 pandemic. Refer to [Table 2-2](#) for more details.

For efficacy endpoints where a change from baseline or percent change from baseline is assessed, only the participants with a baseline and at least one post-baseline value available will be included in the analysis model (number of participants included in the analysis model reported in the table). All available results will be included in the descriptive statistics.

Line plots for change and percent change from baseline will be presented by study intervention group, displaying the LS mean and SE at each visit. These plots will be provided for the primary and all secondary continuous endpoints.

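### Pre-bronchodilator FEV1, one of the two primary endpoints before amendment 03, is outside the testing sequence; before lock it could be added as the last step at no cost to the listed tests

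*SAP*

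**What the plan says.** SAP 8.2.5 sets the overall rule: "The overall type-I error rate will be controlled at the two-sided 0.05 level using a hierarchical testing procedure". There is no alpha split: "Each endpoint will be tested at 0.05 (two-sided) level of significance". SAP 4.1 adds the gate: "After the significance has been achieved for 2 primary endpoints, the other selected secondary endpoints will be tested following a hierarchical testing procedure".

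Putting SAP 8 and 8.2.5 together, the sequence is:

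1. "proportion of participants achieving response of FeNO <25 ppb at Week 24" (CMH test)
2. percent change in untrimmed distal [s]iVaw at TLC (MMRM)
3. change in the global UCSF mucus score
4. percent change in trimmed distal [s]iRaw at TLC

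Steps 3 and 4 are the whole of the list introduced by "The following secondary endpoints will be included in the multiplicity adjustment scheme and tested in the following order".

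The rationale for amended protocol 03 replaces FEV1 with FeNO as a primary endpoint, "leading to an overall reduction in sample size". The SAP document history records that pre-bronchodilator FEV1 moved from primary to secondary, and that post-bronchodilator FEV1 left the testing order. The readable text gives no reason for leaving pre-bronchodilator FEV1 out of the order. It keeps an MMRM (SAP 8.2.1) and two supplementary analyses, outlier removal and borrowing from an earlier Phase 3 study (SAP 8.2.6).

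Protocol 9.4.2 leaves the choice of tested secondary endpoints to the SAP and says that all comparisons will be presented whether or not they can be declared significant.

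**The concern.** In a fixed sequence the full 5% passes to the next hypothesis after each rejection. Here it reaches [s]iRaw and, if that is rejected, goes no further. The endpoint one would expect to find next is absent. The study title says that the effect is assessed "through assessments of lung function, mucus plugging and other lung imaging parameters in patients with asthma", Protocol 2.2 gives the effect on lung function as one of the things the study is designed to assess, and the SAP's own heading for spirometry (8.2.1) uses the term lung function.

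What is at stake is the status of the spirometric result. In a trial where all four listed tests succeed, an FEV1 difference with a small p-value could still not be presented as error-controlled, although the procedure had an unused 5% available for it. A former primary endpoint would be left with nominal analyses only.

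**Working it through.** **Inputs from the documents.** 97 randomized 2:1, 87 evaluable (58 and 29), 10% dropout (SAP 3.1); about 64% power for [s]iVaw with 87 evaluable, two-sample t-test, two-sided 0.05 (Protocol 9.2); each step at two-sided 0.05 (SAP 8.2.5).

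**Not available.** The power assumptions for FeNO and the effect size and SD for [s]iVaw are redacted. No power is given for the mucus score, [s]iRaw or, at the present sample size, FEV1. These are treated below as assumptions over a range.

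**The plan's own figures.** 87 / (1 - 0.10) = 96.7, rounded up to 97, which agrees. The 64% cannot be recomputed without its inputs. Solving a non-central t-test backwards at 58:29 gives an implied standardized effect of 0.533.

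**Cost of a fifth step.** Step 5 is looked at only after steps 1-4 have been rejected, so it cannot alter any of those four decisions. A familywise error requires rejecting the first true null in the order, which happens with probability at most 0.05 however many steps follow. A simulation with 1,000,000 draws, at correlations 0, 0.3 and 0.6, agrees:

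- With the first true null at step 1, 2, 3 or 4, the familywise error was 0.049-0.050 and identical for four and five steps.
- With steps 1-4 all real effects and FEV1 null, the four-step plan has no true null to reject. The five-step plan has an error rate of 0.050, still within the level.
- With assumed powers of 0.95, 0.64, 0.80 and 0.80 and independence, steps 1-4 were rejected with probability 0.950, 0.608, 0.487 and 0.390, both with and without step 5.

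**Chance that FEV1 is formally tested.** All four tests must succeed, so the chance cannot exceed the power of step 2, about 64%. Under independence it is P(FeNO) x 0.64 x P(mucus) x P([s]iRaw):

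- FeNO taken as 1, the other two at 0.60 each: 0.64 x 0.60 x 0.60 = 0.23
- FeNO taken as 1, the other two at 0.90 each: 0.64 x 0.90 x 0.90 = 0.52
- FeNO at 0.80, the other two at 0.64 each: 0.80 x 0.64 x 0.64 x 0.64 = 0.21

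Positive correlation raises these figures. In the simulated example above, the chance of reaching FEV1 is 0.39, 0.47 and 0.54 at correlations 0, 0.3 and 0.6.

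**Chance of a significant FEV1 result.** This also needs FEV1's own power. At 58:29, a two-sample t-test has 26% power for an assumed standardized effect of 0.3, 41% for 0.4, 74% for 0.6 and 86% for 0.7. Under independence the range is then 0.23 x 0.26 = 0.06 to 0.52 x 0.86 = 0.45. If FEV1 had 80% power in the simulated example, the chance of a formal success would go from 0 to 0.31, 0.41 or 0.51 at the three correlations.

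**The case against.** The strongest reply is that this is a design choice the protocol allows. The SAP was given the task of selecting the list, and type I error is controlled for everything on it. Every finite sequence leaves alpha unused after its last step, so the same argument would support adding any unlisted secondary endpoint. This stands: a reader might infer an error-control fault, and there is none. What sets FEV1 apart is its former primary status and its place in the study title.

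A reader might also infer that the study hypothesis concerns FEV1. It does not. The formal hypotheses (Protocol 9.1, SAP 8) cover FeNO <25 ppb and [s]iVaw. The rationale in Protocol 2.1 takes FEV1 changes under dupilumab as already observed and proposes that they are "potentially related to reduction in airway inflammation and changes in airway volumes detectable by functional respiratory imaging". A between-arm FEV1 test does not examine that relationship; the planned correlation analyses do. The protocol also cites an earlier Phase 3 study as having shown the FEV1 effect, which lowers the value of a new claim.

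Nor does the omission bar every claim that touches lung function. Distal airway volume and resistance are both in the sequence, and Protocol 1.1 describes imaging as a more sensitive measure of treatment effect on lung function. The gap is in spirometry.

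Finally, nothing is hidden. The endpoint change is declared with its rationale, and FEV1 will be reported with an estimate, a confidence interval and a Week 24 p-value. The trial was made smaller when FEV1 stopped being primary, so a formal FEV1 test may be underpowered. These points limit the benefit. None of them identifies a statistical cost of adding the step.

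**Conclusion.** This is a free improvement, not an error. As written, the spirometric result is nominal in every trial. With FEV1 as the fifth step it would receive a valid 5% test in at most about 64% of trials, and in about 23-52% under independence with FeNO near certain and 60-90% power for each of the mucus score and [s]iRaw. Only the 64% comes from the documents, and it rests on imaging assumptions that Protocol 9.2 describes as extrapolated from limited data. The percentages are chances of reaching the test. The chance of a significant FEV1 result is lower and cannot be fixed from the documents.

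It might also be inferred that the added step would answer any criticism of the endpoint change. It would not: under the same assumptions FEV1 stays nominal in 48-77% of trials, and in at least 36% because of [s]iVaw alone. The step gives the former primary endpoint a controlled test when the rest of the sequence succeeds, and no more than that.

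**What to change.** Add pre-bronchodilator FEV1 (change at Week 24) to SAP 8.2.5 as the fifth and last test. Name the MMRM of SAP 8.2.1 as its analysis, since Protocol Table 7 and SAP 15.1 refer FEV1 to the imaging model, which lacks the age, height and gender terms of 8.2.1. If the sponsor prefers to leave FEV1 out, a sentence in 8.2.5 giving the reason would serve the reader.

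The cost is one line. The protocol delegates the list to the SAP, and SAP 1 allows revisions before database lock, so the list itself needs no protocol amendment. The power of the listed tests and the 5% bound do not change. The addition is valid only if made before lock and unblinding. The documents do not show whether that window is still open; if it has closed, FEV1 should stay nominal and be labelled so.

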8.2.6. Supplementary analysis

Change from baseline to week 24 in pre-BD FEV₁ will be analyzed as a supplementary analysis in the following ways:

- Removing potential outliers using z-score method

Records with change from baseline value more than 3 standard deviations away from the mean change from baseline for each visit and treatment group will be considered as potential outliers.

Change from baseline will be modelled using an MMRM model under the missing at random framework. The MMRM model will include study intervention (dupilumab, placebo), baseline value of pre-BD FEV₁, region (EE/ROW), ICS dose level (medium/high), visits (up to Week 24), age (years), height (cm), gender (male/female), study intervention by visit interaction, and baseline pre-BD FEV₁ by visit interaction terms all as fixed effects. An unstructured (UN) correlation matrix will be used to model the within-participant errors.

The same strategy as for MMRM model for primary endpoint untrimmed distal [s]iVaw will be used for the selection of the covariance structure if MMRM under unstructured correlation matrix fails to achieve convergence.

- Using data borrowing approach

The Dupilumab Phase III ‘LIBERTY ASTHMA QUEST’ study will be used as the source of historical data, and the propensity score matching method will be implemented first to select appropriate participants, then the Bayesian dynamic borrowing approach will be implemented to evaluate the change from baseline to Week 24 in pre-BD FEV₁. The adjusted LS means in each study intervention group, the LS mean difference between the dupilumab and placebo groups, and the corresponding SE and 95% CI will be provided, and the nominal p-value corresponding to the LS mean difference will be provided for descriptive purpose only.

[figure not shown]
Untrimmed distal [s]iVaw at FRC, trimmed distal [s]iRaw at TLC and trimmed distal [s]iRaw at FRC will be analyzed as a supplementary analysis in the following way:

[figure not shown]
- Removing FRI data with technical issues

Percent change from baseline will be modelled using an MMRM model under the missing at random framework. The MMRM model will include study intervention (dupilumab, placebo), baseline value of the parameter, region (EE/ROW), ICS dose level (medium/high), visits (up to Week 24), study intervention by visit interaction, and baseline value by visit interaction terms all as fixed effects. An unstructured (UN) correlation matrix will be used to model the within-participant errors.

The same strategy as for MMRM model for primary endpoint untrimmed distal [s]iVaw will be used for the selection of the covariance structure if MMRM under unstructured correlation matrix fails to achieve convergence.

9. SAFETY ANALYSIS

All safety results will be summarized using the safety set by actual study intervention group.

The observation periods include:

- The **pre-treatment** period is defined as the time from the signed informed consent date up to first administration of the IMP.
- The **treatment-emergent adverse event (TEAE)** period is defined as the time from the first administration of the IMP (on Day 1) to the last administration of the IMP +98 days and up to the end of the study follow-up.
- The **post-treatment** period is defined as the time starting 1 day after the end of the TEAE period up to the end of the study follow-up.

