9.4.2 Safety analyses

All safety analyses will be performed on the safety population and will be presented by treatment group.

The treatment-emergent is defined as the period of time from the date and time of the first dose of IMP through the date of last dose + 12 weeks (or the day before switch to commercialized dupilumab or other biologic treatment, whichever occurs first).

Table 8 - Safety analyses

Endpoint	Statistical Analysis Methods
Secondary	
 Incidence of TEAEs, TESAEs, TEAE leading to study intervention discontinuation and AESI Adverse event incidence tables will be presented by system organ class (SOC) (sorted by internationally agreed order), high-level group term (HLGT), high level term (HLT) and preferred term (PT), the number (n) and percentage (%) of participants experiencing an AE. Multiple occurrences of the same event in the same participant will be counted only once in the tables. The denominator for computation of percentages is the safety population within each treatment group. Proportion of participants with at least one TEAE, serious TEAE, AESI, and TEAE leading to discontinuation of the study intervention will be tabulated by treatment group. In addition, TEAEs will be described according to maximum intensity and relation to the study drug. Serious AEs and AEs leading to study discontinuation that occur outside the treatment-emergent period will be summarized separately.

Multiplicity Considerations for the secondary endpoints

A multiplicity control procedure and the selected list of secondary endpoints to be tested in the hierarchical order will be specified in the Statistical Analysis Plan. Regardless of eligibility to be declared significant, results for all comparisons will be presented. Descriptive statistics including number of participants, mean, standard deviation, and LS means will also be provided.

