7.1.2. Concomitant medications

Concomitant medications are any treatments received by the participant concomitantly to the IMP, starting from the 1st administration of IMP to the date of last administration +98 days.

The following concomitant medications summaries will be generated separately by study intervention group:

- Inhaled corticosteroids in combination with other controllers summarized by medication type (ICS, LABA, LAMA, LTRA, Other) and standardized medication name.
Note: These medications are recorded in the asthma controller medication eCRF page and ATC codes will be used to categorize them into ICS (ATC class R03BA), LABA (ATC class R03AC), LAMA (ATC class R03BB), LTRA (ATC class R03DC) or Other.
- Reliever (rescue) medications summarized by medication type (SABA, systemic corticosteroids, other) and standardized medication name (see [Section 15.13](#)).
Note: These medications are recorded in the asthma reliever medication eCRF page.
- Other concomitant medications.
Note: These medications are recorded in the other medications eCRF page.

The concomitant prohibited medications will also be presented by prohibited medication category as defined in deviation and standardized medication name (see [Section 15.9](#)).

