9.1. Adverse events

The adverse event types include:

- **Pre-treatment adverse events** are adverse events that developed or worsened or became serious during the pre-treatment period.
- **Treatment-emergent adverse events** are adverse events that developed or worsened or became serious during the TEAE period.
- **Post-treatment adverse events** are adverse events that developed or worsened or became serious during the post-treatment period. AEs categorized as post-treatment AEs (following the rules specified below) will not be summarized.

The primary focus of adverse event reporting will be on TEAEs. Pre-treatment adverse events will be summarized separately.

All AEs will be coded by LLT, PT, HLT, HLGT, and associated primary SOC using the version of Medical Dictionary for Regulatory Activities (MedDRA) currently in effect at Sanofi at the time of each database lock.

Adverse events will be recorded from the time of signed informed consent until the end of the study or the resolution/stabilization of all SAE and AESI.

If an adverse event date/time of onset (occurrence, worsening, or becoming serious) is incomplete, an imputation algorithm will be used to classify the adverse event as pre-treatment, treatment-emergent, or post-treatment. The algorithm for imputing date/time of onset will be conservative and will classify an adverse event as treatment-emergent unless there is definitive information to determine it is pre-treatment or post-treatment. Details on classification of adverse events with missing or partial onset dates are provided in [Section 15.4.5](#).

Adverse events will be summarized by primary SOC, HLGT, HLT, and PT, sorted by internationally agreed order of primary SOC and then alphabetically for the other levels, for each study intervention group using number and percentage of participants experiencing an adverse event. Multiple occurrences of the same event in the same participant will be counted only once in

the tables within an observation period (pre-treatment period or TEAE period). The denominator for computation of percentages will be the safety analysis set within each study intervention group. Participants experiencing asthma exacerbations will be further summarized using the LLT level as appropriate within adverse event summaries.

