9.1.6. Adverse events leading to study discontinuation

Not applicable.

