12. INTERIM ANALYSIS

Not applicable.

13.CHANGES IN THE PLANNED ANALYSIS

Not applicable.

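### The SAP ends the treatment-emergent period at last IMP + 98 days against the protocol's last dose + 12 weeks, and drops the promised summary of late serious AEs

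*SAP*

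**What the plan says.** **End of the period.** Protocol section 9.4.2 starts the treatment-emergent period when dosing begins and carries it "through the date of last dose + 12 weeks (or the day before switch to commercialized dupilumab or other biologic treatment, whichever occurs first". SAP section 9 runs it from the first administration "to the last administration of the IMP +98 days and up to the end of the study follow-up". The SAP applies the same 98 days to concomitant medication, counted "starting from the 1st administration of IMP to the date of last administration +98 days" (section 7.1.2), and starts post-treatment medication on day 99 (section 7.1.3). The SAP section headed "13.CHANGES IN THE PLANNED ANALYSIS" is marked not applicable.

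**Events outside the period.** Protocol Table 8 states: "Serious AEs and AEs leading to study discontinuation that occur outside the treatment-emergent period will be summarized separately". SAP section 9 defines a post-treatment period as "the time starting 1 day after the end of the TEAE period up to the end of the study follow-up", and section 9.1 says that "AEs categorized as post-treatment AEs (following the rules specified below) will not be summarized". SAP section 9.1.6, "Adverse events leading to study discontinuation", is marked not applicable.

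**What the SAP does provide.** Pre-treatment AEs have an overview that includes serious AEs (section 9.1) and a table by SOC and PT (section 9.1.1). Deaths are tabulated by study period, including post-treatment (section 9.1.9). AEs and SAEs are listed individually (section 9.1). Main reasons for study discontinuation appear in the disposition table (section 5.1).

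**The concern.** The incidence of TEAEs and SAEs is the secondary safety endpoint (SAP Table 2-1). Two documents that claim to describe the same analysis give different end dates for its observation period. An event between day 85 and day 98 after the last dose can therefore be treatment-emergent under the SAP and not under the protocol, and no change is declared.

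The second problem does not depend on the day count. The protocol commits to summarising serious events and events leading to study discontinuation that fall outside the period. Under the SAP, a non-fatal serious AE in a participant who stopped IMP early, and whose SAP period has ended, would be visible only in a listing. These participants exist by design: anyone who stops IMP is kept in the study for safety and efficacy (protocol section 7.1.1) and is asked to attend through V5.

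**Working it through.** **Inputs.** Protocol window after last dose: 12 weeks = 12 × 7 = 84 days (section 9.4.2). SAP window: 98 days = 98/7 = 14 weeks (section 9). Week w is Day 1 + 7w, so Week 24 is Day 169 (as in SAP section 15.5) and Week 36, the planned end of follow-up, is Day 253. The two windows differ by 98 - 84 = 14 days; the SAP figure does not follow from the protocol's 12 weeks.

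**Reading of the SAP rule.** I take the reference to the end of follow-up as a cap. SAP section 9 goes on to define a post-treatment period that starts one day later and ends with follow-up, and section 7.1.3 starts post-treatment medication on day 99. Both need a period that stops at day 98 or earlier.

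**Early IMP stopper, last dose at Week w, followed to V5 at Week 24.** Protocol end = min(w + 12, 24). SAP end = min(w + 14, 24). Follow-up left after the SAP period = max(0, 10 - w) weeks.

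| Last dose (week) | Protocol end (week) | SAP end (week) | SAP minus protocol | Left outside the SAP period |
|---|---|---|---|---|
| 0 (Day 1 only) | 12 | 14 | 14 days | 10 weeks |
| 4 | 16 | 18 | 14 days | 6 weeks |
| 8 | 20 | 22 | 14 days | 2 weeks |
| 10 | 22 | 24 | 14 days | 0 |
| 12 | 24 | 24 | 0 | 0 |

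The documents ask these participants to attend up to and including V5. If one were also followed to Week 36 (an assumption), the time left outside would be 36 - (w + 14) = 22 - w weeks, for example 18 weeks for w = 4.

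**Completer followed to Week 36 (Day 253).**

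- Last dose at Week 24 (Day 169): protocol end 169 + 84 = Day 253; SAP end 169 + 98 = Day 267, capped at Day 253. Difference 0 days.
- Last dose at Week 22 (Day 155): protocol end 155 + 84 = Day 239; SAP end 155 + 98 = Day 253. Difference 14 days, or 14/239 = 5.9% of the protocol period.

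**Which last dose is planned?** The documents mostly point to Week 24. SAP section 3.3 continues dosing every two weeks until Week 24. The early-discontinuation visits carry all V5 procedures with IMP excepted (protocol section 1.3 footnotes a and b, and sections 7.1.1 and 7.2), which implies that IMP is planned at V5. SAP section 7.2.1 defines exposure as last minus first dose date + 14 days and has a category above 24 and up to 26 weeks; a Week 24 last dose gives 169 - 1 + 14 = 182 days = 26 weeks, a Week 22 last dose 155 - 1 + 14 = 168 days = 24 weeks. The schedule of activities grid was not legible enough to settle it, so Week 22 stays as an assumption.

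**Outputs compared.** Against the protocol's promise, two items have no SAP counterpart: a summary of post-treatment serious AEs (only the fatal ones reach a table, through deaths by period), and a summary of AEs leading to study discontinuation outside the treatment-emergent period.

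**The case against.** The best defence is that the 98 days are deliberate and harmless. They equal the 14-day dosing interval in the SAP's exposure definition plus the 12-week follow-up; from a Week 22 dose they end exactly at Week 36; and a longer window moves events into the TEAE tables without losing any. With a Week 24 last dose, completers are not affected at all. This stands as a limit on the size. It does not remove the conflict: neither document gives that derivation, the protocol counts from the date of last dose, and section 13 declares nothing.

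Three stronger readings are tempting, and the documents do not support them.

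- *The SAP period runs on to the end of follow-up even after day 98.* The wording alone allows it, but the post-treatment period in SAP section 9 would then be empty, and section 7.1.3 points the same way. No figure should be based on it.
- *Events under commercial dupilumab or another biologic will be counted as treatment-emergent because the SAP has no switch clause.* The cut-off is mostly implied: follow-up ends at a switch (SAP section 3.1), and the V6 call precedes the first commercial injection (protocol section 1.3, footnote d). What remains is a rare deviation: an early stopper who starts a prohibited biologic before V5 and keeps attending.
- *All serious AEs outside the period go unreported.* Pre-treatment serious AEs are summarised, deaths are tabulated by period, and all SAEs are listed.

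**Conclusion.** Wrong as written; minor severity. The undeclared difference between 98 and 84 days is plain on the face of the two documents, and so is the loss of a safety output that the protocol promises. The second holds whichever day count is chosen.

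The size is small. The conflict concerns mainly participants who stop IMP early and stay on study: a 14-day longer SAP period for a last dose at Week 10 or earlier, and 10 - w weeks without an AE summary for a last dose at Week w below 10. This assumes the cap reading and follow-up to V5. For completers it is 0 days on the more likely Week 24 last dose and 14 days on Week 22. The number of participants affected cannot be derived; the protocol expects permanent discontinuation to be rare (section 7.1.1).

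A reader might infer a bias between arms or a threat to the trial's conclusions. Neither follows: the window is the same in both arms, the tables are descriptive, and no hypothesis test uses it.

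**What to change.** 1. Reconcile protocol section 9.4.2 and SAP section 9 into one end rule, stated as the earliest of the agreed number of days after last dose, the day before a biologic switch, and the end of follow-up. Either number of days can be stated clearly; the choice is the sponsor's. Check that the 98 days in SAP sections 7.1.2 and 7.1.3 still agree with it.
2. Add to the SAP a summary by arm of post-treatment serious AEs, and one of AEs leading to study discontinuation outside the treatment-emergent period. Amend sections 9.1 and 9.1.6 to match.
3. Record any remaining departure from the protocol in SAP section 13.

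The cost is a few lines of SAP text and a small added output before database lock, which SAP section 1 allows. No new data collection is needed for the summaries. If the agreed count is not the protocol's 84 days, the protocol wording must change too, or the departure must be declared in section 13.
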